5.2.2. Analysis for Continuous Data

Unless otherwise stated, descriptive statistics for continuous variables are n, mean, median, standard deviation, minimum, and maximum.

5.2.2.1. Geometric Means

The geometric means will be calculated as the mean of the assay results after making the logarithm transformation and then exponentiating the mean to express results on the original scale. Two-sided 95% CIs will be obtained by taking log transformations of assay results, calculating the 95% CI with reference to the Student t distribution, and then exponentiating the confidence limits.

5.2.2.2. Geometric Mean Ratios

Model-Based GMR:

The GMR and the associated 95% CI will be calculated by exponentiating the difference in LS means and the corresponding CIs based on analysis of logarithmically transformed assay results using a linear regression model that includes terms for baseline assay results (log scale), age, and comparison group.

Unadjusted GMR:

The GMR will be calculated as the mean of the difference of logarithmically transformed assay results and exponentiating the mean. Two-sided CIs will be obtained by calculating CIs using the Student t distribution for the mean difference of the logarithmically transformed assay results and exponentiating the confidence limits.

5.2.2.3. Geometric Mean Fold Rises

GMFRs are defined as ratios of the results after vaccination to the results before vaccination. GMFRs are limited to participants with nonmissing values at both time points. GMFRs will be calculated as the mean of the difference of logarithmically transformed assay results (later time point minus earlier time point) and exponentiating the mean. The associated 2-sided 95% CIs will be obtained by constructing CIs using the Student t distribution for the mean difference on the logarithm scale and exponentiating the confidence limits.

5.2.2.4. Reverse Cumulative Distribution Curves

Empirical RCDCs will plot proportions of participants with values equal to or exceeding a specified assay value versus the indicated assay value, for all observed assay values. Data points will be joined by a step function with data points on the left side of the step.

5.3. Methods to Manage Missing Data

In general, completely missing reactogenicity data (ie, all 7 days of collection were missing and no reactogenicity events were reported on the AE CRF) will not be imputed. For partially missing reactogenicity data (eg, 1-6 days of reactogenicity data are available), it is assumed that no reactions or events were experienced on the missing days.

A partial AE start date (missing day or missing both month and day) will be imputed by assigning the earliest possible start date using all available information, such as the stop date of the AE and the study vaccination date(s) from the same participant, following the Pfizer standard for handling an incomplete AE start date. A completely missing start date for an AE is not allowed in the data collection.

Missing serology results will not be imputed. Immunogenicity results that are below the LLOQ will be set to $0.5 \times \text{LLOQ}$ in the analysis; this may be adjusted once additional data on the assay characteristics become available.

No additional imputation will be applied to other missing data.

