# 6.4.2. Blinding of Site Personnel

Investigators and other site staff will be unblinded to participants' assigned study intervention.

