# 8.3.4. Electronic Diary

All participants will be required to complete a reactogenicity e-diary after vaccination given at Visit 1, through an application installed on a provisioned device or on the participant's own personal device. All participants will be asked to monitor and record local reactions, systemic events, and use of any medication for solicited pain symptoms or fever for 7 days, or longer for ongoing symptoms, from the day of administration of the study intervention given at Visit 1. The reactogenicity e-diary allows recording of these assessments each day, thus providing the accurate representation of the participant's experience. Data on local reactions and systemic events reported in the reactogenicity e-diary will be transferred electronically to a third-party vendor, where they will be available for review by investigators and the Pfizer clinicians at all times via an internet-based portal.

At intervals agreed to by the vendor and Pfizer, these data will be transferred electronically into Pfizer's database for analysis and reporting. Generally, these data do not need to be reported by the investigator in the CRF as AEs. However, if a participant has a serious adverse event reported in the e-diary, the event(s) should be recorded on the CRF, regardless of whether the investigator considers the event(s) to be related. If a participant missed reporting an event in the e-diary and reports it to the study site instead, the event should also be recorded on the CRF.

Investigators (or designee) will be required to review the reactogenicity e-diary data online at frequent intervals to evaluate participant compliance and as part of the ongoing safety review.

The investigator or designee must obtain stop dates from the participant for any symptoms ongoing on the last day from Day 7 onwards and follow up daily until resolution. The stop dates should be documented in the source documents and the information entered in the CRF.

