# 9.5. Sample Size Determination

The sample size is not based on any formal hypothesis test. All statistical analyses will be descriptive.

For safety outcomes, Table 7 shows the probability of observing at least 1 AE for a given true event rate of a particular AE. For example, if the true AE rate is 1%, with approximately 160 participants in a vaccine group, there is 80% probability of observing at least 1 AE.

Table 7. Probability of Observing at Least 1 AE, by Assumed True Event Rate

Assumed True Event Rate of an	N=20	N=80	N=160	N=640
AE				
0.1%	0.02	0.08	0.15	0.47
0.5%	0.10	0.33	0.55	0.96
1%	0.18	0.55	0.80	>0.99
2%	0.33	0.80	0.96	>0.99
3%	0.46	0.91	0.99	>0.99
4%	0.56	0.96	>0.99	>0.99
5%	0.64	0.98	>0.99	>0.99

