2.2. Study Objectives, Endpoints, and Estimands

The estimands corresponding to the primary objectives are described in Table 2.

The safety primary objective evaluations are based on the safety population. In general, completely missing reactogenicity data (ie, all 7 days of collection were missing) will not be imputed. For partially missing reactogenicity data (eg, 1-6 days of reactogenicity data are available), it is assumed that no reactions or events were experienced on the missing days. Missing AE start dates will be imputed according to Pfizer safety rules. No other missing information will be imputed in the safety analysis.

The estimands to evaluate the immunogenicity objective are based on the evaluable immunogenicity population (Section 4). These estimands estimate the vaccine effect in the hypothetical setting where participants follow the study schedules and protocol requirements as directed. Missing antibody results will not be imputed. Immunogenicity results that are below the LLOQ will be set to $0.5 \times LLOQ$ in the analysis. This may be adjusted once additional data on the assay characteristics become available.

Table 2. List of Primary and Exploratory Objectives, Endpoints, and Estimands

| Objectives | Endpoints | Estimands |
|--|---|---|
| Primary: | Primary: | Primary: |
| Safety | | |
| To describe the safety and tolerability of the study interventions | Local reactions (pain at the injection site, redness, and swelling) Systemic events (fever, fatigue, headache, chills, | The percentage of participants receiving at least 1 dose of study intervention reporting: Local reactions for up to 7 days following vaccination |

Table 2. List of Primary and Exploratory Objectives, Endpoints, and Estimands

| Objectives | Endpoints | Estimands |
|--|---|---|
| | vomiting, diarrhea, new or worsened muscle pain, and new or worsened joint pain) • AEs • SAEs | Systemic events for up to 7 days following vaccination AEs from vaccination through 4 weeks after vaccination SAEs from vaccination through 6 months after vaccination |
| Immunogenicity | | |

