3.1.1.1. Local Reactions

The local reactions assessed and reported in the e-diary are redness, swelling, and pain at the injection site, from Day 1 through Day 7 after vaccination, where Day 1 is the day of the vaccination. If a local reaction persists beyond the end of the 7-day e-diary collection period following vaccination, the participant will be requested to report that information and/or any new reactogenicity reactions that develop to the investigator or the study staff. The investigator will enter this additional information in the CRF.

Presence or Absence

For each local reaction and any local reaction on any day, Table 4 explains the algorithm to derive the presence of a reaction (yes or no) during the interval from Day 1 through Day 7, where Day 1 is the day of the study vaccination.

Table 4. Derived Variables for Presence of Each and Any Local Reaction Within 7 Days for the Study Vaccination

| Variable | Yes (1) | No (0) |
|---|--------------------------|--|
| Presence of each local reaction on any day. | reaction as "yes" on any | Participant reports the reaction as "no" on all 7 days (Day 1 through Day 7) or as a combination of "no" and missing on all 7 days (Day 1 through Day 7). |
| Presence of any local reaction on any day. | reaction as "yes" on any | For all 3 local reactions, participant reports "no" on all 7 days (Day 1 through Day 7) or as a combination of "no" and missing on all 7 days (Day 1 through Day 7). |

Note: Completely missing reactogenicity data will not be imputed. Participants with no reactogenicity data reported will not be included in the reactogenicity summaries.

Severity and Maximum Severity

Redness and swelling will be measured and recorded in measuring device units (range: 1 to 21) and then categorized during analysis as absent, mild, moderate, or severe based on the grading scale in Table 5. Measuring device units can be converted to centimeters according to the following formula: 1 measuring device unit = 0.5 cm. Pain at the injection site will be assessed by the participant as absent, mild, moderate, or severe according to the grading scale in Table 5.

Table 5. Local Reaction Grading Scale

| | Mild (Grade 1) | Moderate (Grade 2) | Severe (Grade 3) | Potentially Life-Threatening (Grade 4) |
|----------------------------|--|---|---|--|

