6. ANALYSES AND SUMMARIES

6.1. Primary Endpoints

6.1.1. Safety Primary Endpoints

6.1.1.1. Local Reactions

6.1.1.1.1. Main Analysis

- Estimand: The percentage of participants reporting local reactions (redness, swelling, and pain at the injection site) for up to 7 days following vaccination (Section 2.2).
- Analysis set: Safety population (Section 4).
- Analysis time point: Up to 7 days following vaccination.
- Analysis methodology: Descriptive statistics (Section 5.2.1).
- Intercurrent events and missing data: Missing data will be handled as described in Section 5.3.
- Reporting results: Descriptive statistics for each and any local reaction after vaccination in each arm (left and right deltoid) will be presented by maximum severity and cumulatively across severity levels for each vaccine group. Descriptive summary statistics will include counts and percentages of participants with the indicated endpoint and the associated 2-sided Clopper-Pearson 95% CIs.

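### SAP 5.3 adds a CRF condition to the definition of completely missing reactogenicity data, so inclusion of participants with no e-diary data can depend on whether they had an event

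*SAP*

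**What the plan says.** The SAP carries two definitions of completely missing reactogenicity data.

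- SAP Section 2.2 says that "completely missing reactogenicity data (ie, all 7 days of collection were missing) will not be imputed". Protocol Section 9.1.1 has the same definition.
- SAP Section 5.3 applies the term only when "all 7 days of collection were missing and no reactogenicity events were reported on the AE CRF".
- SAP Section 2.1 declares no modification to the analysis described in the protocol.

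The main analysis of local reactions (SAP Section 6.1.1.1.1) takes its estimand from Section 2.2, and for missing data it states: "Missing data will be handled as described in Section 5.3". The systemic event analysis (Section 6.1.1.2.1) does the same. Both definitions are therefore invoked within one primary analysis.

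The consequence for the denominator is stated in the note under SAP Table 4 (Section 3.1.1.1): "Participants with no reactogenicity data reported will not be included in the reactogenicity summaries".

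The protocol provides a route from a missed diary entry to the CRF. Under Section 8.3.4, when a participant misses an event in the diary and "reports it to the study site instead, the event should also be recorded on the CRF". Section 8.10.1 also sends acute reactions seen during post-vaccination observation to the CRF. Neither section describes a matching CRF entry that records the absence of a reaction.

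**The concern.** The CRF can supply cases among participants with no diary data, but it does not supply non-cases. If a CRF event is what moves such a participant from excluded to included, everyone who enters by that route has an event, and inclusion depends on the outcome being measured.

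Local and systemic reaction percentages are primary safety endpoints, and the four groups are meant to be compared. The site staff who make CRF entries know the allocation. Protocol Section 6.4.2 says: "Investigators and other site staff will be unblinded to participants' assigned study intervention". CRF capture could therefore differ between groups.

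Table 4 adds a second gap. Its 'No' value needs 'no' on all 7 days, or a mixture of 'no' and missing. A participant with nothing in the diary and one reaction on the CRF meets neither condition for the other reactions, so their status is undefined.

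**Working it through.** **1. Group size.** Protocol Section 9.5 says that "with approximately 160 participants in a vaccine group, there is 80% probability of observing at least 1 AE", for a true rate of 1%. Check: 1 − 0.99^160 = 0.7997, which agrees. This only fixes N at about 160 per group. The documents state no figure for non-transmission or CRF capture, so both are assumed below.

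**2. The two rules side by side**, each read with the Table 4 note, for a participant with no diary data on any of the 7 days:

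| AE CRF | SAP 2.2 and Protocol 9.1.1 | SAP 5.3 |
|---|---|---|
| Reactogenicity event recorded | Completely missing, left out | Not completely missing, can be counted as a case |
| No reactogenicity event recorded | Completely missing, left out | Completely missing, left out |

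**3. Effect if entry is decided reaction by reaction.** Let p be the true rate, m the share with no diary data (taken as unrelated to outcome) and q the share of events in those participants that reach the CRF.

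- SAP 2.2 rule: (1−m)p / (1−m) = p.
- SAP 5.3 rule: [(1−m)p + mpq] / [(1−m) + mpq].

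For p = 50% under the SAP 5.3 rule:

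| m | q = 25% | q = 50% | q = 100% |
|---|---|---|---|
| 5% | 0.48125/0.95625 = 50.3% | 0.4875/0.9625 = 50.6% | 0.500/0.975 = 51.3% |
| 10% | 0.4625/0.9125 = 50.7% | 0.475/0.925 = 51.4% | 0.500/0.950 = 52.6% |

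In counts with N = 160 and full capture (Clopper-Pearson 95% CI):

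- 8 without diary data: 76/152 = 50.0% (41.8 to 58.2) against 80/156 = 51.3% (43.2 to 59.4).
- 16 without diary data: 72/144 = 50.0% (41.6 to 58.4) against 80/152 = 52.6% (44.4 to 60.8).

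Over p from 10% to 70%, m from 2% to 10% and q from 25% to 100%, the shift is 0.05 to 2.6 percentage points upward.

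**4. Effect if any CRF event admits the participant to every denominator.** Let a be the share of non-transmitters admitted in this way, and count unrecorded reactions as 'No'. The rate is [(1−m)p + mpq] / [(1−m) + ma]. Take p = 5%, q = 100% and a = 70% (assumed):

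- m = 5%: 0.05/0.985 = 5.08%, against 0.05/0.9525 = 5.25% with reaction-specific entry.
- m = 10%: 0.05/0.970 = 5.15%, against 0.05/0.905 = 5.52%.

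The rate falls below p whenever q is less than a. In the extreme case q = 0 with m = 10% and a = 70%, it is 0.045/0.970 = 4.64%.

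**5. Unequal capture between groups.** Suppose two groups have the same true rate (10% to 70%) and reaction-specific entry, one with full capture and the other with none. The spurious difference is 0.5 to 1.3 points at m = 5% and 1.0 to 2.6 points at m = 10%. This is the extreme case.

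**The case against.** The case for leaving the text alone has real content.

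- **Section 5.3 speaks only of imputation.** It does not say who is admitted or dropped, and the named analysis set is the whole safety population. This stands as a description of Section 5.3. The selection follows only when the Table 4 note is added, but that note does remove participants with no data.
- **Section 5.3 may be a clarification.** Section 2.2 refers to days of collection without naming the e-diary, and a CRF event is arguably reported data, so the Table 4 note fits Section 5.3 without strain. That is a possible reading. Even so, it leaves the CRF condition absent from Section 2.2 and the protocol, and the selection on outcome remains.
- **Keeping known reactions is conservative.** The estimand is not limited to diary reports, and Grade 4 systemic events and fevers above 40.0°C are collected on the CRF. This is a good reason to keep such events visible. It does not require mixing them into a percentage that has no matching non-cases.
- **The situation may be rare.** Protocol Section 8.3.4 describes a missed event, not a week with no transmission. Sites review diaries, ideally daily, and SAP Section 6.6.2.3 tabulates transmission. This stands: the route exists, but its frequency is unknown.
- **The study is descriptive.** No hypothesis or decision rule is affected. This also stands, and it limits the severity.

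**Conclusion.** The inconsistency is in the text and touches primary safety endpoints. With reaction-specific entry, its likely effect is a fraction of a percentage point up to about 2.6 points, where the 95% interval at this group size extends roughly 8 points either side. The size depends on assumed non-transmission and capture, on non-transmission being unrelated to outcome, and on the entry rule, which the SAP does not state. It is worth correcting before the first analysis, but it does not undermine the study.

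A reader might infer three stronger conclusions that the documents do not support.

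- **That every reactogenicity percentage is biased upward.** This holds for reaction-specific entry. If any CRF event admits a participant to all denominators, a poorly captured reaction can be diluted.
- **That uncommon reactions are inflated by 5% to 10% in relative terms.** This needs full capture and reaction-specific entry. With participant-level entry and 70% having any event, the figure is about 1.5% to 3%.
- **That the confidence intervals describe no defined population.** The population can be stated as vaccinated participants with reactogenicity data from diary or CRF. Its weakness is that, for participants without diary data, membership depends on having had an event.

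**What to change.** Use one definition in SAP Sections 2.2, 3.1.1.1 and 5.3. Completely missing would mean no e-diary reactogenicity data on any of the 7 days, and the main-analysis denominator would be vaccinated participants with at least one such day. SAP Section 3.5.2 already has a close definition of a transmitted e-diary, although it also counts a diary that holds only medication use, so the wording should say which applies.

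Show CRF-only events in non-transmitters, including any Grade 4 event, in a separate row or listing beside the main table. Add them to the percentages in a sensitivity analysis.

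If the sponsor prefers to keep the CRF clause, it should be recorded in SAP Section 2.1 as a change from Protocol Section 9.1.1. The SAP should then say whether entry is by reaction or by participant, and Table 4 should define the remaining reactions of a CRF-only participant.

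The cost is a few sentences, one row or listing and one sensitivity table. The downside is that a few CRF-only events leave the main percentage, but they remain reported.

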6. ANALYSES AND SUMMARIES

6.1. Primary Endpoints

6.1.1. Safety Primary Endpoints

6.1.1.1. Local Reactions

6.1.1.1.1. Main Analysis

- Estimand: The percentage of participants reporting local reactions (redness, swelling, and pain at the injection site) for up to 7 days following vaccination (Section 2.2).
- Analysis set: Safety population (Section 4).
- Analysis time point: Up to 7 days following vaccination.
- Analysis methodology: Descriptive statistics (Section 5.2.1).
- Intercurrent events and missing data: Missing data will be handled as described in Section 5.3.
- Reporting results: Descriptive statistics for each and any local reaction after vaccination in each arm (left and right deltoid) will be presented by maximum severity and cumulatively across severity levels for each vaccine group. Descriptive summary statistics will include counts and percentages of participants with the indicated endpoint and the associated 2-sided Clopper-Pearson 95% CIs.

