#### 6.1.1. Administration

Standard vaccination practices must be observed and vaccine must not be injected into blood vessels. Appropriate medication and other supportive measures for management of an acute hypersensitivity reaction must be available in accordance with local guidelines for standard immunization practices.

Administration of study interventions will be performed by an appropriately qualified, trained, and vaccine-experienced member of the study staff (eg, physician, nurse, physician's assistant, nurse practitioner, pharmacist, or medical assistant) as allowed by local, state, and institutional guidance.

Study intervention administration details will be recorded on the CRF.

Participants will receive 2 injections at Visit 1 as randomized in accordance with the SoA. Study intervention should be administered intramuscularly into the deltoid muscle of the appropriate arm as detailed in Table 3, and in such a way as to ensure that the participants remain blinded.

**Table 3.** Anatomical Location for Study Intervention Administration

Vaccine Group Number	Left Deltoida	Right Deltoid a
1	BNT162b2 (Omi XBB.1.5)/RIV	Placebo
2	BNT162b2 (Omi XBB.1.5)	RIV
3	BNT162b2 (Omi XBB.1.5)	Placebo
4	RIV	Placebo

a. Study intervention will be administered in contralateral arms. Local reactions will be assessed at the injection site on both the left and right deltoids.

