#### 8.3.4.2. Local Reactions

During the reactogenicity e-diary reporting period, participants will be asked to assess redness, swelling, and pain at each injection site and to record the symptoms in the reactogenicity e-diary.

If a local reaction persists beyond the end of the 7-day e-diary collection period following vaccination, the participant will be requested to report that information and/or any new reactogenicity reactions that develop to the investigator or the study staff. The investigator will enter this additional information in the CRF.

Participants will be provided with a measuring device. Redness and swelling will be measured and recorded in measuring device units (range: 1 to 21) and then categorized during analysis as absent, mild, moderate, or severe based on the grading scale in Table 4. Measuring device units can be converted to centimeters according to the following formula: 1 measuring device unit = 0.5 cm. Pain at the injection site will be assessed by the participant as absent, mild, moderate, or severe according to the grading scale in Table 4.

If a Grade 3 local reaction is reported in the reactogenicity e-diary, a telephone contact should occur to ascertain further details and determine whether a site visit is clinically indicated. Only an investigator or medically qualified person is able to classify a participant's local reaction as Grade 4. If a participant experiences a confirmed Grade 4 local reaction, the investigator must immediately notify the sponsor.

**Table 4.** Local Reaction Grading Scale

	Mild (Grade 1)	Moderate (Grade 2)	Severe (Grade 3)	Potentially Life-Threatening (Grade 4)
Pain at the injection site	Does not interfere with activity	Interferes with activity	Prevents daily activity	Emergency room visit or hospitalization for severe pain
Redness	>2.0 cm to 5.0 cm (5 to 10 measuring device units)	>5.0 cm to 10.0 cm (11 to 20 measuring device units)	>10 cm (≥21 measuring device units)	Necrosis or exfoliative dermatitis

	Mild (Grade 1)	Moderate (Grade 2)	Severe (Grade 3)	Potentially Life-Threatening (Grade 4)
Swelling	>2.0 cm to 5.0 cm (5 to 10 measuring device units)	>5.0 cm to 10.0 cm (11 to 20 measuring	>10 cm (≥21 measuring device units)	Necrosis

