2.3. Study Design

This is a Phase 1/2 single-blind (site- and sponsor-unblinded) study to evaluate the safety, tolerability, and immunogenicity of licensed BNT162b2 (Omi XBB.1.5) and RIV administered together as a single injection (referred to as BNT162b2 [Omi XBB.1.5]/RIV) in healthy adults 50 years of age or older.

The safety, tolerability, and immunogenicity of BNT162b2 (Omi XBB.1.5)/RIV administered as a single injection will be compared to BNT162b2 (Omi XBB.1.5) and RIV administered simultaneously as 2 separate injections (coadministered), and to BNT162b2 (Omi XBB.1.5) or RIV when administered alone.

Across Phases 1 and 2, approximately 640 participants in total will be randomized with an equal randomization ratio (1:1:1:1) to each of the following vaccine groups and stratified by age group (50 through 64 years of age and ≥65 years of age):

- **Group 1:** BNT162b2 (Omi XBB.1.5)/RIV (as a single injection) administered in the left deltoid and placebo administered in the right deltoid
- **Group 2:** BNT162b2 (Omi XBB.1.5) administered in the left deltoid and RIV administered in the right deltoid
- **Group 3:** BNT162b2 (Omi XBB.1.5) administered in the left deltoid and placebo administered in the right deltoid
- **Group 4:** RIV administered in the left deltoid and placebo administered in the right deltoid

Figure 1. Study Schema

| Phase 1 N = 80 | | | | | |
|--|--|---|-------------------|--|--|
| Group 1 BNT162b2/RIV (1.0 mL) + | Group 4 RIV (0.5 mL) + placebo (0.5 mL) | | | | |
| placebo (0.5 mL) | BNT162b2 (0.3 mL) Phase 1a (Participants 50 | placebo (0.5 mL) O through 64 years of age | placebo (0.5 mL) | | |
| Sentinel $n = 10$ | Sentinel $n = 10$ | Sentinel $n = 10$ | Sentinel $n = 10$ | | |
| Sponsor Safety Data Review ^a Phase 1b (Participants ≥65 years of age) | | | | | |
| n = 10 $n = 10$ $n = 10$ $n = 10$ | | | | | |
| Phase 2 N = 560 Participants ≥50 years of age | | | | | |
| n = 140 $n = 140$ $n = 140$ $n = 140$ | | | | | |

- a. Progression of the study will occur upon confirmation of an acceptable safety assessment of data accumulated after at least 24 hours and up to 7 days after vaccination.
- Progression of the study will occur upon confirmation of an acceptable safety assessment of data accumulated after at least 72 hours and up to 7 days after vaccination, once approximately 20 participants in each vaccine group have been vaccinated.

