| Pain at the injection site | Does not interfere with activity | Interferes with activity | Prevents daily activity | Emergency room visit or hospitalization for severe pain |
| Redness | >2.0 cm to 5.0 cm (5 to 10 measuring device units) | >5.0 cm to 10.0 cm (11 to 20 measuring device units) | >10 cm (≥21 measuring device units) | Necrosis or exfoliative dermatitis |
| Swelling | >2.0 cm to 5.0 cm (5 to 10 measuring device units) | >5.0 cm to 10.0 cm (11 to 20 measuring device units) | >10 cm (≥21 measuring device units) | Necrosis |

If a Grade 3 local reaction is reported in the reactogenicity e-diary, a telephone contact should occur to ascertain further details and determine whether a site visit is clinically indicated. Only an investigator or medically qualified person is able to classify a participant's local reaction as Grade 4. If a participant experiences a confirmed Grade 4 local reaction, the investigator must immediately notify the sponsor. A Grade 4 reaction will be collected on the CRF.

For each local reaction reported after the study vaccination, the maximum severity grade will be derived for the e-diary collection period (Day 1 through Day 7, where Day 1 is the day of the vaccination) as follows:

• Maximum severity grade = highest grade (maximum severity) within 7 days after administration (Day 1 through Day 7) among severity grades reported for that local reaction.

Duration (First to Last Day Reported)

The duration (days) of each local reaction will be calculated as the number of days from the start of the first reported reaction to the resolution of the last reported reaction, inclusive (last day of reaction - first day of reaction + 1). Resolution is defined as the last day on which the reaction is recorded in the e-diary or CRF. If there is no known date when the reaction ended, then duration will be missing (unknown). Participants with no reported reaction have no duration.

Onset Day

The onset day of each local reaction will be derived. Onset day is defined as the first day of reporting any severity.

For the onset day of each local reaction, if participants report change in severity of the local reaction, only the first day of reporting that specific local reaction will be counted.

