6.1.1.1.2. Supplemental Analysis

To support the assessment of local reactions, the following endpoints (as defined in Section 3.1.1.1) will be summarized with the same analysis time point and analysis population as above and the appropriate analysis methodology and reporting results:

- Duration (days) of each local reaction after vaccination in each arm (left and right deltoid).
- Onset day of each local reaction after vaccination in each arm (left and right deltoid).

These continuous endpoints will be summarized by displaying n, mean, median, standard deviation, minimum, and maximum for each vaccine group.

Figures:

Bar charts with the proportions of participants for each local reaction throughout 7 days after vaccination in each arm (left and right deltoid) will be plotted for each vaccine group. The bars will be divided into severity categories to highlight the proportions of participants by maximum severity.

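### The local-reaction estimand counts participants, but every local-reaction output in the SAP is per deltoid and no either-site summary is specified

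*SAP*

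**What the plan says.** SAP 6.1.1.1.1 states the estimand as "The percentage of participants reporting local reactions (redness, swelling, and pain at the injection site) for up to 7 days following vaccination". Protocol Section 3 also counts participants, and neither text names an injection site.

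Every participant receives two injections, one per deltoid. Protocol 6.1.1 (Table 3, footnote a) says: "Local reactions will be assessed at the injection site on both the left and right deltoids". Protocol 8.3.4.2 has participants assess "redness, swelling, and pain at each injection site and to record the symptoms in the reactogenicity e-diary". Both sites are therefore recorded in all four groups.

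The outputs are by site. The main table is "Descriptive statistics for each and any local reaction after vaccination in each arm (left and right deltoid) will be presented by maximum severity". SAP 6.1.1.1.2 lists "Duration (days) of each local reaction after vaccination in each arm (left and right deltoid"), and onset day and the bar charts carry the same by-arm qualifier. SAP 6.5 repeats the primary endpoints by age group without adding a site rule.

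The derivations are in SAP 3.1.1.1. The negative cell of Table 4 for any reaction begins "For all 3 local reactions, participant reports" and then combines the three reaction types over seven days. Maximum severity is the "highest grade (maximum severity) within 7 days after administration (Day 1 through Day 7) among severity grades reported for that local reaction". Neither mentions site.

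On the purpose of the groups, SAP 2.3 says the combination "administered as a single injection will be compared to BNT162b2 (Omi XBB.1.5) and RIV administered simultaneously as 2 separate injections (coadministered"), and it lists safety and tolerability among the things compared.

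**The concern.** An estimand that counts participants needs one yes/no value per participant. With two sites per person, someone has to decide how left and right make that value. The SAP does not decide it, and it lists no table in which the participant-level percentage would appear.

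For Groups 1, 3 and 4 the right arm holds placebo, so the left-arm rate will often be close to the participant-level rate. In Group 2 both arms hold active vaccine and the two can differ substantially. A reader who wants to know whether one combined injection leaves more or fewer people with a sore arm than two separate injections cannot get that from the per-arm tables. Two programmers could also reasonably build different variables from Table 4, one pooling sites and one not.

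**Working it through.** **Inputs.** Group size is 20 + 140 = 160 (protocol Table 2; SAP Table 3). The interval for a rate is Clopper-Pearson and that for a difference is Miettinen-Nurminen, both two-sided 95% (SAP 5.2.1). The documents contain no local-reaction rates and no either-site figure, so there is no plan figure to reproduce on this point. All rates below are assumed.

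**Step 1: what two per-arm rates determine.** Let L and R be the left- and right-arm rates. The either-site rate E satisfies max(L, R) ≤ E ≤ min(1, L + R). It equals 1 - (1 - L)(1 - R) if the sites are independent. It equals the lower bound if everyone who reacts in the less reactive arm also reacts in the other (nested). For example, L = 60% and R = 40% give E anywhere from 60% to 100%, and 76% under independence. With placebo on the right, L = 60% and R = 10% give only 60% to 70%, and 64% under independence. The gap is therefore widest for Group 2.

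**Step 2: Group 1 minus Group 2.** Assume Group 1 has 65%/10% and Group 2 has 60%/30%, with the same type of dependence between sites in both groups.

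| Dependence | Group 1 | Group 2 | Counts of 160 | Difference in points (95% CI) |
|---|---|---|---|---|
| Nested | 65% | 60% | 104 vs 96 | +5.0 (-5.6 to 15.5) |
| Independent | 1 - 0.35 × 0.90 = 68.5% | 1 - 0.40 × 0.70 = 72.0% | 110 vs 115 | -3.1 (-13.1 to 6.9); unrounded -3.5 |
| Disjoint (extreme bound) | 75% | 90% | 120 vs 144 | -15.0 (-23.3 to -6.8) |

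With a common between-site odds ratio (Plackett form), the difference is -3.5 at an odds ratio of 1, -1.4 at 2, 0.0 at 3.3, +1.1 at 5 and +2.6 at 10. Recomputed at each of these values with counts rounded to whole participants, every 95% interval includes zero.

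**Step 3: other assumed rates.** Group 1 stays at 65%/10%.

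- Group 2 at 40%/20%: nested 65 - 40 = +25.0; independent 68.5 - 52.0 = +16.5; disjoint 75 - 60 = +15.0.
- Group 2 at 70%/40%: nested 65 - 70 = -5.0; independent 68.5 - 82.0 = -13.5. A disjoint pattern is impossible here because the two rates sum to 110%.

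In both cases the size moves with the dependence and the sign does not.

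**The case against.** The strongest reply is that the endpoint is already defined. Protocol Section 3 counts participants, protocol 9.3.2 promises statistics for each reactogenicity endpoint by vaccine group without restricting them to a deltoid, SAP 2.1 declares no departure from the protocol, and Table 4 is worded per participant. On that reading, someone who reacts at either site is a participant with a reaction, and the by-arm wording only adds detail. In addition, the *Yes* cells of Table 4 are cut off in the text available for this review, so half of each presence definition cannot be read in full.

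Much of this stands. Pooling the sites is a natural reading and nothing forbids an either-site table. But no legible sentence states the rule. Even if Table 4 does pool, the reporting bullet applies each and any reaction within each arm, so the pooled variable reaches no listed output.

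A second reply is that the comparison carries little weight. The primary safety objective is to describe, there is no hypothesis test, the between-group objective is exploratory and concerns immune responses, and the SAP's group contrasts (6.1.2.1.2 and 6.1.2.2.2) cover only immunogenicity. That is correct. The statement about comparing one injection with two is general design language. The case for the change rests on reporting the stated estimand, with the Group 1 and Group 2 contrast as the place where its absence is felt most.

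A third reply is that per-arm tables are the better tool for attributing reactions to a product, and that an either-site rate mixes in placebo-site reactions in Groups 1, 3 and 4. Both points are true. They are reasons to keep the per-arm tables and footnote the new one.

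**Conclusion.** The gap is real but limited. A primary safety estimand stated per participant has no specified output at that level, and the specified per-arm rates only bound it.

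Its size depends on rates the documents do not give. In the 65%/10% versus 60%/30% illustration, the either-site difference ranges over 8.5 points (-3.5 to +5.0) between independent and nested sites, and the 95% intervals, about 20 points wide, include zero throughout. The -15.0 figure requires that a reaction in one arm exclude a reaction in the other for every participant in both groups, which nothing in the documents supports. It is a bound only.

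Three stronger readings are tempting and not supported. One is that the per-arm tables generally leave open which approach is better tolerated: the change of sign is a product of the chosen rates and did not occur in the two other sets tried. Another is that the endpoint is undefined: its unit is clear, and only the combination rule and the table are missing. The third is that a planned local-reaction comparison is compromised: none is planned. Confidence is high that the summary is not listed, and lower about its practical impact.

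**What to change.** Keep all per-arm tables. In SAP 3.1.1.1, define a participant-level variable for each reaction and for any reaction: present if reported at either site, with maximum severity the highest grade across both sites. In SAP 6.1.1.1.1, report it by vaccine group with the Clopper-Pearson 95% interval as the summary of the stated estimand, and note that it includes placebo-site reactions in Groups 1, 3 and 4. Duration and onset day may stay by arm.

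This is a cheap improvement: one derived variable and a few table rows, from data already collected, with no change to visits or sample size. The downside is slightly longer tables. Because site and sponsor staff are unblinded (protocol 6.4.2 and 6.4.3), it is better to fix the rule in the SAP than to choose it once the data have been seen.
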